1.1 Summary

1.2 Synopsis

Title of the study:	
Phase I clinical study, to evaluate the safety and tolerability of the ophthalmic solution PRO-179 compared with Travatan®, on the ocular surface of clinically healthy subjects.	
Protocol code: SOPH179-0818/I	Creation date: August 1, 2018
Protocol version: 1	Date of the version: August 1, 2018.
Therapeutic indication: Ocular hypotensor	Use: Primary open-angle glaucoma
Estimated duration of the study (from the first visit of the first patient to the preparation of the final report): 4 months	Development phase: I
Goals: To evaluate the safety and tolerability of the formulation PRO-179 manufactured by Laboratorios Sophia S.A. of C.V. on the ocular surface of clinically healthy subjects.	
Hypothesis: The ophthalmic solution PRO-179 presents a profile of safety and tolerability similar to Travatan® in healthy subjects.	
Methodology: Clinical trial Phase I, controlled, of parallel groups, double blind, with randomization.	
Number of patients: n= 24 12 subjects per group (both eyes).	Main inclusion criteria: Clinically healthy subjects.
Main selection criteria: Inclusion criteria:	

 - Be clinically healthy. - Have the ability to give their signed informed consent and show willingness to comply with the study procedures - Have an age between 18 to 45 years. - Indistinct sex. - Women should ensure the continued use of a hormonal contraceptive method or intrauterine device (IUD) during the study period. - Present blood tests: within normal parameters or with a range of \pm 20% as long as the subject is clinically healthy. 	

- Blood count (BH): Hemoglobin, erythrocytes, hematocrit, total leukocytes, platelets, mean corpuscular volume and mean corpuscular hemoglobin.
- Blood chemistry of three elements (QS): Glucose, urea and creatinine.
- Liver function tests (PFH): TGO, TGP, total bilirubin, direct and indirect.
- Present visual ability 20/30 or better in both eyes.
- Present vital signs within normal parameters.
- Present intraocular pressure ≥ 10 and ≤ 21 mmHg.

Exclusion criteria:

- Be a user of topical ophthalmic products of any kind.
- Be a user of medicines, or herbal products, by any other route of administration, with the exception of hormonal contraceptives in the case of women.
- In case of being a woman, being pregnant or breastfeeding.
- Have participated in clinical research studies 90 days prior to inclusion in the present study.

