The data will be expressed with measures of central tendency: mean and standard deviation for the quantitative variables. The qualitative variables will be presented in frequencies and percentages. The statistical analysis will be carried out by means of the Mann-Whitney U test for the quantitative variables for the difference between the groups. The difference between the qualitative variables will be analyzed by means of χ^2 (Chi2) or Fisher's exact. An alpha ≤ 0.05 will be considered significant.

1.2 Diagram of the study.

* Baseline measurements can be taken from those made during the screening visit. It is the investigator's prerogative to perform them again at the baseline visit.

1.3 Schedule of the study .

Procedures	Scrutiny D 1 - X ^a	VB D 1	V1 D 5 ± 1	VF D 11 a + 1	LIS D 14 ± 1
CI Signature	X				
Clinic history	X				
Concomitant Medication Evaluation	X	X	X	X	
Urine pregnancy test	X			X	
Vital signs	X	X ¹	X	X	
CV	X	X ¹	X	X	
Integrity of the ocular surface	X	X ¹	X	X	
PIO	X	X ¹	X	X	
Comprehensive ophthalmological evaluation	X	X ^{1,2}	X	X ²	
Eligibility criteria	X	X ^b			
Blood sampling	X			X	
EA evaluation	X	X	X	X	X
Review of laboratory results		X			X
Assignment of Research Product (PI)		X			
Ocular Comfort Index		X		X	
Delivery of the IP and start of intervention		X			
Adherence evaluation			X	X	
Daily delivery of the subject		X	X		
Continuity evaluation of the subject			X		
Return / Evaluation of the subject's Journal			X	X	
Return of IP				X	

- a. The counting visit may be up to 7 days before the baseline, if it exceeds these the subject can not enter.
- b. These criteria will be completed with the results of the laboratory tests and those obtained during the screening visit. 1 They can be taken from the scrutiny visit, it is the prerogative of the PI to measure them again at the baseline visit. 2 Includes subsequent segment valuation.

**Page intentionally left
blank**

2 Content

1.1 SUMMARY	1
1.2 SYNOPSIS	1
1.2 DIAGRAM OF THE STUDY.	4
1.3 SCHEDULE OF THE STUDY .	5
2 CONTENT	7
3 INDEX OF ABBREVIATIONS.	11
4 ADMINISTRATIVE STRUCTURE OF THE STUDY.	13
5 INTRODUCTION	15
5.1 THEORETICAL FRAMEWORK.	15
5.2 BACKGROUND .	15
5.2.1 PHARMACOLOGY OF TRAVOPROST.	15
5.2.1.1 Pharmacokinetics .	16
5.2.1.2 Pharmacodynamics .	16
5.2.2 EFFICIENCY OF TRAVOPROST.	16
5.2.3 SAFETY OF TRAVOPROST.	17
5.2.4 RISK BENEFIT EVALUATION.	17
5.2.4.1 Known potential risks.	17
5.2.4.2 Known potential benefits.	17
5.3 STATEMENT OF THE PROBLEM.	17

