- Compare the safety of PRO-179 with Travatan® by the incidence of chemosis during visits.
- Compare the safety of PRO-179 with Travatan® by means of the incidence of alterations in the results of the laboratory tests on day 11.

- Compare the safety of PRO-179 with Travatan® through the incidence of changes in HR during visits.
- Compare the safety of PRO-179 with Travatan® by means of the incidence of RF alterations during visits.
- Compare the safety of PRO-179 with Travatan® by the incidence of changes in SAD during visits.

5.5.3 Exploratory objectives.

- Compare changes in intraocular pressure during visits.

5.5.4 Hypothesis.

H0 The ophthalmic solution PRO-179 presents a profile of safety and tolerability similar to Travatan® in healthy subjects.

Ha The ophthalmic solution PRO-179 presents a different safety and tolerability profile Travatan® in healthy subjects.

5.6 Design and plan of the study.

Clinical trial, phase I, controlled, of parallel groups, double blind with randomization.

5.6.1 Discussion of the study design.

The design of the study (clinical trial) is considered the highest standard of data quality when looking to explore the effect of an intervention. The phase of pharmacological development (phase I) corresponds to the objective of the study which is to assess safety and tolerability, so that the intervention time is short and the sample size required is less than that of a clinical efficacy trial. The presence of parallel groups allows the comparison between the intervention groups on the outcome variables. Blinding and randomisation allow to reduce biases that are incurred with other designs, eg. selection bias, evaluation bias, among others.

The comparator, Travatan®, has a known safety profile and shares the same active principles in the same concentrations as PRO-179, which is why it was chosen as the best option to compare.

5.6.2 Justification of the posology.

The chosen dosage is one drop every 24 hours at night, this is the indicated and approved dosage for the reference medicine. Clinical studies demonstrate the sufficiency of 1 drop every 24 hours; likewise, they have shown that the administration at night presents less IOP fluctuations during 24 hours, unlike the morning application. [38]

For this phase I study, we do not consider it necessary to expose the research subjects to dosage rates higher than those recommended, since it is not justifiable.

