The return will be made by the research center when the sponsor indicates it. Prior to the return, the research center must make a count of the assigned medication and the remaining medication, with the aim of creating an inventory which serves for the final filling of the medication return form.

6.4 Delay variables.

6.4.1 Security variables.

6.4.1.1 Primary outcome variables.

- Incidence of adverse events.

6.4.1.2 Variables of primary outcome of tolerability.

- ICO score.

6.4.1.3 Secondary outcome variables.

- Changes in visual ability.
- Changes in corneal and conjunctival staining with lysine green.
- Changes in corneal and conjunctival staining with fluorescein.
- Changes conjunctival hyperemia.
- Incidence of chemosis.
- Incidence of alterations in the results of laboratory tests.
- Incidence of alterations in the FC.
- Incidence of alterations in the RF.
- Incidence of alterations in the TAS.

6.4.2 Exploratory variables.

- Changes in IOP.

6.4.3 Methods and scales to be used for the measurement of the variables.

Variable	Kind	Unit (Symbol)	Method of measurement	Normal value	Evaluation time	Statistical test
Primary						
Adverse events	Discreet Categorical rating	Number of cases (n) Present/absent	Count Observation	0 Absent	VB, V1, VF y LLS	Mann-Whitney U χ^2 o Fisher's exact
ICO score	Discreet	Points	Questionnaire	NA	VB, VF	Mann-Whitney U
Secondary						
Visual ability	Discreet	Fraction	Snellen Primer	1	VB, V1 y VF	Mann-Whitney U
Corneal and conjunctival staining with fluorescein	Ordinal	Degrees	Direct observation with slit lamp and cobalt blue filter, Oxford scale graduation	0	VB, V1 y VF	χ^2 or Fisher's exact

Variable	Kind	Unit (Symbol)	Method of measurement	Normal value	Evaluation time	Statistical test
Corneal and conjunctival staining with lysamine green	Ordinal	degrees	Direct observation with slit lamp, Oxford scale graduation	0	VB, V1 y VF	χ^2 or Fisher's exact
Conjunctival hyperemia	Ordinal	Normal / Very Light / Mild / Moderate / Severe	Direct observation. Classification of Efron.	Normal	VB, V1 y VF	χ^2 or Fisher's exact
Chemosis	Categorical rating	Present / absent		Absent	VB, V1 y VF	χ^2 or Fisher's exact
FC	Discreet	eats per minute (l / m)	Auscultation with stethoscope	60 to 100	VB, V1 y VF	Mann-Whitney U
FR	Discreet	Breaths per minute (r / m)	Auscultation with stethoscope	12 to 24	VB, V1 y VF	Mann-Whitney U
TAS	Discreet	Millimeters of mercury (mmHg)	Measurement with sphygmomanometer	90-120/ 60-80	VB, V1 y VF	Mann-Whitney U

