Calculation: the percentage of AD presented in the group treated with travoprost was considered. Expecting a similar proportion of conjunctival hyperemia due to PGA and healthy subjects. Considering a power of 80%, a significance level of 0.05 (α) and a non-inferiority margin of 5% (δ).

Calculated sample: 20, increasing the calculation by 20% considering possible losses, 25 subjects.

Suggested sample: 12 subjects (24 eyes) per treatment arm.

6.7 Recruitment.

It is essential that, if necessary during the development of this research protocol, the principal investigator requests the approval of the Research Ethics Committee and the Research Committee, as well as the authorization of COFEPRIS, to publish or disseminate in mass media, the invitation to participate in the study to those people who meet the selection criteria.

It is possible to discuss with other health professionals the opportunity for healthy subjects to be evaluated by an ophthalmologist at no cost, as well as cabinet exams that will allow the more accurate determination of their ocular clinical status by participating in a sponsored clinical research protocol by Sophia Laboratories, SA of C.V.

7 Methods. Assignment of the intervention.

7.1 Generation of the allocation sequence.

Two strata corresponding to the intervention groups will be used, which will be balanced for a research center. The allocation will be 1: 1. The generation will be carried out by a third party, authorized by Sophia Laboratories, S.A. of C.V., through its electronic system. The information corresponding to this third party will be found in the file.

7.2 Blinding mechanism.

Blinding will be done by the Department of Clinical Operations of Sophia Laboratories, S.A. of C.V. Which will consist of the elimination of the primary label (commercial) in the case of Travatan® and the placement of a label identical to the other IP. Because the bottle in which Travatan® is packaged differs in color and shape to that used for PRO-179, a masking will be made in the primary packaging which will be identical for the interventions. The subject will have determinedly prohibited to comment with another person that is not the pharmacist aspects related to the primary container (bottle).

7.3 Implementation.

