- Intra-group analysis: will be determined by the Wilcoxon rank test, for quantitative variables [65]
- Inter-group analysis: will be determined by the Mann-Whitney U test Kruskal-Wallis. This non-parametric test will be used to test whether a group of data comes from the same

population. Intuitively, it is identical to the ANOVA with the data replaced by categories using the student's t statistic.

The level of difference to consider significance will be an alpha of 0.05 or less.

The result of nominal and ordinal qualitative variables will be presented in frequencies, proportions and percentages, see table 3 (section 6.4.3).

The statistical analysis to identify significant differences of the qualitative variables will be done creating 2x2 contingency tables and it will be done in the following way:

- Intra-group difference: McNemar test [66]. Which is applied to 2×2 contingency tables with a dichotomous trait, with pairs of matched subjects, to determine if the marginal frequencies of row and column are equal (marginal homogeneity).
- Inter-group difference: Pearson's χ^2 test (or Fisher's exact).

The level of difference to consider significance will be an alpha of 0.05 or less.

For the reporting of adverse events all eyes of those participants who were randomly assigned to an intervention group after the baseline visit will be considered. The results will be expressed in number of cases (eyes).

The final report of the results will be shown in tables or graphs, as appropriate.

It will be considered that the investigational drug is safe and tolerable when there are no clinical and statistical differences in all the variables of primary outcome, with respect to its comparators.

Those subjects who comply with an adherence greater than 60% will be included in the statistical analysis to meet the objective of the study, taken from the subject's diary. It was considered that from the minimum dose necessary to obtain a pharmacological effect (hypotensive / 1 application per day) and the presence of adverse events (exposure) is sufficient to meet the overall design objective, according to the pharmacological characteristics of the IP.

8.3.2 Additional analyzes.

No additional analyzes are contemplated to those previously described. Nevertheless, these may be performed if during the conduction of the study it is required to analyze specific safety aspects of any intervention, maintaining the blinding until the end of the study.

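### Section 8.3.1 declares PRO-179 safe and tolerable when no differences are found, but with 12 subjects per arm and no threshold, margin or confidence interval, a non-significant result is not evidence of similarity

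*Combined protocol and SAP*

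**What the plan says.** - **Decision rule (8.3.1).** PRO-179 is to be regarded as safe and tolerable on this condition: "the investigational drug is safe and tolerable when there are no clinical and statistical differences in all the variables of primary outcome".
- **Hypotheses.** Section 5.5.4 makes similarity the null: "H0 The ophthalmic solution PRO-179 presents a profile of safety and tolerability similar to Travatan® in healthy subjects". The alternative is a different profile. The synopsis states similarity as the study hypothesis.
- **Tests.** Section 8.3.1 plans Mann-Whitney for quantitative variables and Pearson chi-square or Fisher's exact for qualitative ones, with no rule for choosing between the last two. The synopsis says "An alpha ≤ 0.05 will be considered significant".
- **Margin.** A 5% non-inferiority margin appears in 6.6.1 for sizing only. Section 8.3 does not use it.
- **Size (6.6.1).** "Suggested sample: 12 subjects (24 eyes) per treatment arm".
- **Unit of the adverse event test.** Section 8.3.1 expresses adverse event results as counts of eyes. Table 3 (6.4.3) gives the unit only as "Number of cases (n) Present/absent". Neither says whether the 2x2 test is by eye or by subject.
- **Absent.** There is no clinically relevant difference for adverse event incidence or for the Ocular Comfort Index (ICO), and no confidence interval for either.

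**The concern.** The favourable conclusion is what remains when the null is not rejected. In a small trial that is the usual outcome whether or not the products differ.

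The rule also mentions clinical differences, which could act as a safeguard. Without a stated size, that part would be judged after the results are seen. Only p>0.05 can be applied reproducibly.

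At stake is the study's main conclusion. Section 5.4 says the trial is meant to document the safety and tolerability of a generic, and 5.3 says that published equivalence data for such products are scarce. A report following 8.3.1 could claim more than its data show.

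**Working it through.** **Inputs from the protocol.** 12 subjects (24 eyes) per arm; alpha 0.05, taken as two-sided for the difference tests; margin 5 points; power 80%. Base rates: hyperemia 12.9% and ocular adverse events 41.9% (6.6.1, glaucoma patients), hyperemia 27% and 49% (5.2.3). **Assumed:** the size of the true rise, any clinical threshold, and the correlation between a subject's two eyes.

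**1. The plan's own sample size.** The 6.6.1 formula with k=1 is n per arm = [pA(1-pA) + pB(1-pB)] x [(z(1-alpha) + z(1-beta)) / (pA - pB - delta)]^2, with 1.645 + 0.842 = 2.4865 after rounding.

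- The stated 20 is recovered only by entering two different outcomes as the two arms' rates: (0.129 x 0.871 + 0.419 x 0.581) x (2.4865/0.34)^2 = 0.3558 x 53.48 = 19.03, rounded up to 20. Then 20/(1 - 0.2) = 25. In this formula 20 is a per-arm figure.
- With equal rates in the arms, n = 2p(1-p) x (2.4865/0.05)^2. This gives 556 per arm at 12.9%, 975 at 27%, 1,205 at 41.9% and 1,237 at 49%. The trial has 12.

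**2. Statistical part of the rule: chance of p>0.05 in the adverse event test.** Every possible 2x2 table was enumerated. By subject, counts are binomial(12). By eye, 12 subjects contribute two eyes each, with inter-eye correlation 0 to 1. Ranges run from uncorrected chi-square to Fisher over the four base rates.

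| True rise on PRO-179 | By subject (12 v 12) | By eye (24 v 24) |
|---|---|---|
| +20 points | 81-91% | 56-79% |
| +30 points | 63-79% | 33-53% |
| +40 points | 41-61% | 11-30% |

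The by-eye test is itself invalid. With equal true rates and a subject's two eyes always agreeing, it rejects in 8-22% of trials instead of 5%.

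The open choice of test can decide the result. Observed 2/12 v 7/12 gives Fisher p = 0.089. Uncorrected chi-square is 24 x (2x5 - 7x10)^2 / (12 x 12 x 9 x 15) = 4.44, p = 0.035.

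**3. Adding a clinical part.** Suppose an observed excess at or above a threshold counts as a clinical difference. The chance of passing both parts for adverse event incidence, given a true +30 points, is:

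| Threshold (assumed) | By subject | By eye |
|---|---|---|
| 10 points | 15-18% | 5-18% |
| 20 points | 29-31% | 18-31% |
| 30 points | 47-48% | 33-53% |

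**4. What 12 per arm can exclude.** Newcombe intervals for the difference:

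- 0/12 v 0/12 leaves an upper limit of 24 points (two-sided 95%) or 18 points (one-sided 0.05).
- With truly equal rates, the upper limit falls below 5 points in only 4-5% of trials (two-sided 95%) or 8-11% (one-sided 0.05, as in the 6.6.1 formula).

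**Not computed.** The whole rule also needs no difference in ICO and in the adverse event count. Those tests can only lower the pass rates above. The protocol gives no distribution for either, so the reduction cannot be quantified.

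**The case against.** **The clinical part protects, and the document does contain a threshold.** The strongest form of this argument takes the 5% margin of 6.6.1 as the clinical limit on the observed excess. A true +30 points would then pass the adverse event part in only 7-9% of trials by subject and 3-10% by eye, and +40 points in 2-3% by subject. This stands as arithmetic, and it shows that the figures in step 2 describe the p-value alone. But 8.3.1 does not adopt that reading, and even under it a true +20 points passes in 17-21% of trials by subject.

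**Phase I trials are not powered for this.** True, and nothing here asks for more subjects. A small descriptive study is legitimate. A conclusion drawn from non-significance is not.

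**The eye-level problem works against the sponsor.** Ignoring the correlation produces false differences and makes the favourable conclusion harder to reach. That is correct, and the 8-22% is the extreme case: at correlation 0.5 it is 6-13%. It is still a reason to fix the unit.

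**Equal rates in the two arms are assumed.** The similarity expected in 6.6.1 can be read as patients against healthy subjects. The per-arm sizes of 556 and above are therefore conditional on equal rates.

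**Consequences are limited.** Section 5.4 says PRO-179 is already registered, and nothing ties a regulatory decision to this rule. The harm is an overstated conclusion, but it is the trial's main one.

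**Conclusion.** The concern holds. Following 8.3.1 as written can produce a conclusion of safety and tolerability that the data do not support. This is an error in the rule, not a missing detail, and it should be corrected before the data are analysed.

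The statistical part alone would usually be met by subject at a true rise of 20 or 30 points. How far the clinical part would reduce this cannot be known, because the plan gives no threshold. These figures cover adverse event incidence only and rest on assumed rises and thresholds, with base rates partly from glaucoma patients. The logical point does not depend on them.

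The statement that no margin exists applies to the decision rule. The protocol has one in 6.6.1, but it is unused in 8.3 and out of reach with 24 subjects.

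**What to change.** 1. **8.3.1:** delete the sentence that makes absence of differences the proof of safety and tolerability.
2. **5.5.4 and synopsis:** replace the similar/different hypotheses with a descriptive objective, to estimate the differences between PRO-179 and Travatan.
3. **8.3.1:** report the subject-level difference in adverse event incidence (PRO-179 minus Travatan; Newcombe or Miettinen-Nurminen) and the Hodges-Lehmann difference in ICO, each with a 95% confidence interval. Name the analysis population for each, and say whether ICO is the day-11 score listed in the synopsis or the change from baseline.
4. **8.3.1 and the adverse event row of Table 3:** make the between-group comparison by subject, with eye counts descriptive only.
5. **8.3.1 and synopsis methods:** state that p>0.05 is not evidence of similarity, and label p-values exploratory.
6. **6.6.1:** state that the 5% margin is not tested and that 24 subjects cannot realistically exclude it.

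Keeping a comparative claim with a pre-stated margin is possible in principle. With equal rates, 80% power and one-sided 0.05, the smallest margin that 12 per arm supports is 2.4865 x sqrt(2p(1-p)/12): 34 points at 12.9% and 50 points at 41.9%. The descriptive route is therefore the practical one.

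**Cost:** protocol and synopsis wording plus two confidence intervals on data already planned, with no new visits or subjects. The downside is that the report can no longer claim demonstrated similarity.

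### The success rule in 8.3.1 has no direction, so a significant and clinically relevant advantage for PRO-179 would deny the conclusion that it is safe and tolerable

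*Combined protocol and SAP*

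**What the plan says.** Section 8.3.1 contains the protocol's only success rule. The investigational drug is to be regarded as safe and tolerable "when there are no clinical and statistical differences in all the variables of primary outcome, with respect to its comparators". The two primary variables are the incidence of adverse events and the ICO score (Synopsis; 6.4.1.1 and 6.4.1.2).

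The hypotheses in 5.5.4 match that rule. The null is "H0 The ophthalmic solution PRO-179 presents a profile of safety and tolerability similar to Travatan® in healthy subjects"; under the alternative the product "presents a different safety and tolerability profile". The tests in 8.3.1 are also non-directional: "The statistical analysis to identify significant differences of the qualitative variables will be done creating 2x2 contingency tables", with Mann-Whitney U for quantitative variables. On the threshold the plan says only "The level of difference to consider significance will be an alpha of 0.05 or less"; it never states whether tests are one-sided or two-sided.

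Section 6.6.1 is the only place with a direction. It prints a one-directional pair of hypotheses for pA − pB against δ and names "a non-inferiority margin of 5" per cent. It does not say which product is A and which is B. The margin does not reappear in the analysis section or in the success rule. Nowhere is a difference in PRO-179's favour exempted.

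**The concern.** The verdict has a direction. More adverse events or more ocular discomfort speak against a product being safe and tolerable; fewer events or less discomfort do not. The rule ignores this. If PRO-179 did clearly better than Travatan on either primary variable, the literal result would be that safety and tolerability had not been shown.

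This is a false-negative fault. It differs from the better-known weakness of the same sentence, which is that a non-significant result in a small trial passes as evidence of safety. What is at stake here is a conclusion that contradicts the data in the one case where the data favour the test product, and the temptation to reinterpret the rule once the results are known.

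**Working it through.** **Inputs.** 12 subjects per arm, allocation 1:1 (6.6.1, 7.1). Fisher's exact or Pearson's χ², α = 0.05 (8.3.1), read as two-sided because the alternative in 5.5.4 is non-directional. Rates of 12.9% (conjunctival hyperemia) and 41.9% (all ocular adverse events, 13/31) are printed in 6.6.1. The 27% used below is an assumption for illustration.

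**The plan's own figure.** The plan gives no operating characteristic for its success rule. Its sample size of 20 can be reproduced with the formula in 6.6.1 if pA = 0.129, pB = 0.419, k = 1, one-sided α = 0.05, power 80% and δ = 0.05. That assignment is inferred, not stated:

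(0.129 × 0.871 + 0.419 × 0.581) × [(1.645 + 0.842) / (0.129 − 0.419 − 0.05)]² = 0.3558 × 53.48 = 19.03, rounded up to 20; 20 / 0.8 = 25.

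This shows where the 12.9% v 41.9% contrast may have entered the plan. It is not evidence that one product has the lower rate: both figures come from a single travoprost arm and describe two different endpoints.

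**Which results trip the rule.** With 5 events among 24 subjects, the chance that all fall in one given arm is C(12,5)/C(24,5) = 792/42,504 = 0.0186. Doubling gives a two-sided Fisher p of 0.037. So 0/12 on PRO-179 v 5/12 on Travatan is significant. So are 1/12 v 7/12 (p = 0.027) and 2/12 v 8/12 (p = 0.036). The mirror-image results against PRO-179 have the same p-values, so the statistical part of the rule cannot tell better from worse.

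**How often.** The chance that the adverse-event variable breaks the rule because of a result favouring PRO-179 is

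P = Σ Bin(t; 12, pPRO) × Bin(c; 12, pTrav), summed over all t < c with p(t, c) ≤ 0.05,

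where t and c are the numbers of subjects with an event on PRO-179 and on Travatan. Exact enumeration, with χ² uncorrected, gives:

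| True rates, PRO-179 v Travatan | Fisher | χ² |
|---|---|---|
| 12.9% v 12.9% | 0.25% | 1.2% |
| 41.9% v 41.9% | 1.1% | 3% |
| 27% v 41.9% (assumed) | 6% | 12% |
| 12.9% v 41.9% (assumed) | 21% | 35% |

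These count every significant result as breaking the rule and cover the subject-level present/absent test only. Section 8.3.1 reports adverse events by eye. Treating 24 eyes per arm as independent would raise the last Fisher figure to 53%, but it counts two eyes of one person as two persons, so the subject-level figures are used here.

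**The case against.** The best defence is that the rule and the hypotheses agree. PRO-179 is a generic with the same active principle at the same concentration, and 5.5.4 asks whether its profile is similar to Travatan's. For that question a difference in either direction counts against similarity. This stands: the rule is not wrong in itself. The fault is that a similarity rule is attached to a verdict of safe and tolerable.

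A second defence is the wording. If a difference must be both clinical and statistical to break the rule, a significant but trivial advantage might pass. That also stands, although a significant and clinically relevant advantage fails under either reading. On adverse events the escape is narrow, since Fisher significance at 12 per arm needs a gap of at least five subjects.

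Three stronger readings are tempting, and the documents do not support them.

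- A reader might infer that 6.6.1 states outright that only an excess on PRO-179 matters, so that 5.5.4 should simply adopt its hypotheses. It leaves A and B undefined. If A is PRO-179 and p is an adverse-event rate, its printed alternative (pA − pB > δ) describes excess harm, not non-inferiority. Only the name given to the margin points to non-inferiority.
- A reader might take 21% to 35% as the expected failure rate. That needs PRO-179 at 12.9% and Travatan at 41.9%, whereas 6.6.1 expects a similar proportion of hyperemia.
- A reader might want one figure for all the primary tests together. The protocol gives no ICO distribution or event-count distribution from which to compute it.

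The practical consequence is also limited. The product already holds a registration (5.4), no later decision is tied to the sentence, and an advantage would be visible in the reported tables.

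**Conclusion.** The point holds as a mismatch between a two-directional rule and a one-directional conclusion, and it is minor. As written, a significant and clinically relevant advantage for PRO-179 on either primary variable denies the conclusion, and no text prevents this. On the subject-level adverse-event test the chance is at most about 3% when the products share a rate of 12.9% or 41.9%; it becomes appreciable only if PRO-179 is truly much better. The figures assume two-sided testing, 12 evaluable subjects per arm and independent subjects, and they leave out the ICO score and the test on event counts.

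**What to change.** In 8.3.1, state that only a difference unfavourable to PRO-179 (more subjects with adverse events, or a worse ICO score) counts against the conclusion, and that differences in its favour are reported but do not block it.

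In 5.5.4, word the alternative explicitly as PRO-179 having a worse safety and tolerability profile than Travatan. Do not copy the hypotheses printed in 6.6.1 while their arms remain undefined.

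The cost is one sentence in each section, made before unblinding. Sample size, visits and data collection do not change.

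This does not repair the reading of non-significance as proof of safety. With true event rates of 41.9% on PRO-179 and 12.9% on Travatan, Fisher's test at 12 per arm would detect the harm in only 21% of trials, so the adverse-event criterion would still be met in about 79%. That needs its own remedy.
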